Assessments collected at unscheduled visits will only be listed, except in the case of determining treatment-emergent markedly abnormal criteria for laboratory and vital sign parameters where all post-Baseline (scheduled and unscheduled) values will be summarized. For PK, immunological and immunogenicity analyses, SFU data will be a part of the data reported in some tables ([Section 9](#)).

For by-visit tables summarizing efficacy data, the SFU visit will not be included, but SFU efficacy data will be listed. By-visit tables summarizing safety will however include the SFU visit.

A complete set of data listings containing all documented data and all derived data (eg, change from Baseline) will be generated.

Repeated visits will not be summarized but listed.

Unless otherwise stated, listings will be sorted by treatment, subject number within each treatment group (not randomization number), variable (if applicable) and visit (if applicable, including timing relative to dosing if applicable). For listings including nonrandomized subjects, the nonrandomized subjects will be shown first in the listing, ordered by subject number. All listings will include repeat and unscheduled measurements; such measurements will appear in chronological order together with the scheduled visits, ie, a repeated measurement will appear directly after the visit and time relative to dosing for which the repeat measurement was performed. In all the listings dates will be presented in the format 'YYYY-MM-DD' and times will be presented in 24h clock format as 'hh:mm'.

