10.3 Clinical laboratory evaluations

The list of the laboratory measurements/variables that will be evaluated in the study is specified in [Table 10–2](#) per laboratory category.

Table 10–2: Laboratory measurements

Hematology	Biochemistry	Urinalysis
Basophils	Calcium	pH
Eosinophils	Chloride	Albumin (protein)
Lymphocytes	Magnesium	Glucose
Monocytes	Potassium	Blood
Neutrophils	Sodium	Leukocyte esterase
Hematocrit	Glucose	Nitrite
Hemoglobin	BUN	Urine dipstick for pregnancy testing ^b
MCH	Creatinine	Urine drug screen ^c
MCHC	hs-CRP	
MCV	AST	

Hematology	Biochemistry	Urinalysis
Platelet count	ALT	
RBC count	GGT	
WBC count	ALP	
	Total bilirubin	
	Triglycerides ^a	
	Cholesterol ^a	
	HDL cholesterol ^a	
	LDL cholesterol ^a	
	LDH	
	Serum pregnancy testing ^b	

ALP=alkaline phosphatase; ALT=alanine aminotransferase; AST=aspartate aminotransferase; BUN=blood urea nitrogen; CRP=C-reactive protein; ET=early termination; GGT=gamma-glutamyltransferase; HDL=high density lipoprotein, IMP=investigational medicinal product; LDH=lactate dehydrogenase; MCH=mean corpuscular hemoglobin; MCHC=mean corpuscular hemoglobin concentration; MCV=mean corpuscular volume; RBC=red blood cell; SFU=Safety Follow-Up; WBC=white blood cell.

^a Biochemistry will include triglycerides, cholesterol, HDL cholesterol, and LDL cholesterol at Baseline, Weeks 12 and 24, and at the ET Visit.

^b Pregnancy testing will consist of serum testing at the Screening Visit for all women of childbearing potential. The pregnancy test will be urine at all other visits.

^c Urine drug screen will be performed at Screening Visit.

Biochemistry and hematology values will be flagged based on their reference range:

- Values that are below the lower limit of the reference range will be flagged as ‘L’ (low)
- Values that are above the upper limit of the reference range will be flagged as ‘H’ (high)
- All other values will be referenced as normal.

Markedly abnormal values for blood chemistry and hematology will be defined as laboratory values graded 3 or 4 according to the Rheumatology Common Toxicity Criteria (RCTC).

Definitions of the markedly abnormal values are given in [Table 10–3](#) and [Table 10–4](#) and are based on the RCTC units. All units in the tables below will be converted to the standard units based on Clinical Data Interchange Standards Consortium (CDISC) standards.

Table 10–3: Definitions of markedly abnormal biochemistry values

Parameter name	Unit	Criteria	Abnormal designation

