Creatinine	mmol/L	>3.0 x ULN or >3.0 x Baseline	AH
Glucose	mmol/L	<2.2 >13.9	AL AH
Calcium	mmol/L	>3.1 <1.75	AH AL

Parameter name	Unit	Criteria	Abnormal designation
Magnesium	mmol/L	>1.23	AH
		<0.4	AL
Potassium	mmol/L	>6.0	AH
		<3.0	AL
Sodium	mmol/L	>155	AH
		<130	AL
Triglyceride	mmol/L	>5.7	AH
Cholesterol	mmol/L	>10.34	AH

AH=abnormal high; AL=abnormal low; dL = deciliter; L = liter;
mg = milligram; mmol = millimoles; ULN = upper limit of normal.

Table 10–4: Definitions of markedly abnormal hematology values

Parameter name	Unit	Criteria	Abnormal Designation
Hemoglobin	g/L	<80	AL
		>40 above ULN or >40 above Baseline if Baseline is above ULN	AH
Lymphocytes Absolute	10 ⁹ /L	<0.5	AL
		>20.0	AH
Neutrophils Absolute	10 ⁹ /L	<1.0	AL
Platelets	10 ⁹ /L	<50	AL
WBC/ Leukocytes	10 ⁹ /L	<2.0	AL
		>100	AH

Definitions of the markedly abnormal values for liver enzyme elevation are given in [Table 10–5](#).

Table 10–5: Definitions of markedly abnormal liver enzyme elevation values

Parameter name	Unit	Criteria	Abnormal Designation
Alkaline Phosphatase		>5.0 x ULN	AH
ALT	U/L	>5.0 x ULN	AH
AST	U/L	>5.0 x ULN	AH
Total Bilirubin	umol/L	>3.0 x ULN	AH
GGT	U/L	>5.0 x ULN	AH

ALT= alanine aminotransferase; AST = aspartate aminotransferase; GGT=gamma-glutamyltransferase.

All laboratory summaries will be presented in standard international (SI) units and will be based on observed case values. In the case where laboratory values are below the lower limit of quantification, then these will be set to the midpoint between 0 and the lower limit of quantification for the purpose of summarizing the data.

In the case where laboratory data are expressed as above a fixed value (ie, “>xx.xx”), then the numeric portion of the value will be used (ie, : xx.xx) to present and calculate statistics.

To define the minimum/maximum post-Baseline values, all post-Baseline assessments including those at unscheduled visits (but excluding any that occur more than 140 days after the last administration of study medication) will be used.

Different summary tables for hematology, biochemistry variables (except hs-CRP which will be analyzed in the efficacy section) and urinalysis (pH, Albumin (protein), glucose, blood, leukocyte esterase and nitrite) will be provided in the SS. For shift tables, results for the treatment period will be presented together for the overall study period.

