As indicated in [Section 3.1](#), for tables where data are summarized by visit only values occurring at scheduled visits will be included.

For each laboratory parameter, the below results will be presented for the overall study period, by treatment group:

- Observed values at Baseline and observed values and changes from Baseline at each scheduled post-Baseline visit.
- Number and percentage of subjects by CTCAE grade (version 4.03) (when applicable) based on the minimum/maximum post-Baseline value (for blood chemistry and hematology).
- Shift in CTCAE grade from Baseline to minimum/maximum post-Baseline (for blood chemistry and hematology). Subjects who meet the decreased potassium criterion of 3.0-<LLN, which is specified as the decreased potassium lab criterion for both CTCAE Grade 1 and Grade 2, will be counted as Grade 2.
- Number and percentage of subjects meeting the below criteria at any time during the study:
 - AST: >2xULN, >3xULN, >5xULN, >10xULN, >20xULN

- ALT: >2xULN, >3xULN, >5xULN, >10xULN, >20xULN
- AST or ALT: >2xULN, >3xULN, >5xULN, >10xULN, >20xULN
- Bilirubin: >1xULN, >1.5xULN
- ALP: >2xULN
- Number and percentage of subjects with potential Hy's Law cases based on the two following definitions:
 - [AST \geq 3xULN or ALT \geq 3xULN] and Total Bilirubin \geq 2xULN
 - [AST \geq 3xULN or ALT \geq 3xULN] and Total Bilirubin \geq 2xULN in the absence of ALP \geq 2xULN

In order to meet either of the above criteria, a subject must experience the elevation in bilirubin and ALT or AST (and the absence of ALP elevation, if applicable) at the same visit.

The below results will be presented on the SS. All values observed at any time while on treatment (ie, occurring at scheduled and unscheduled visits) will be included in the below tables. Baseline values and values observed more than 140 days after the last administration of study medication are not considered:

- Number and percentage of subjects with treatment emergent markedly abnormal laboratory data overall (for blood chemistry and hematology). All values observed at any time while on treatment (ie, occurring at scheduled and unscheduled visits) will be included in this table summarizing markedly abnormal values. For this summary, Baseline values and values observed more than 140 days after the last administration of study medication are not considered.

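### The 'treatment emergent' markedly abnormal laboratory table has no comparison with Baseline, so abnormalities that predate dosing and persist are counted as emerging on treatment

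*SAP*

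**What the plan says.** Section 10.3 defines markedly abnormal chemistry and hematology results by the Rheumatology Common Toxicity Criteria (RCTC): they "will be defined as laboratory values graded 3 or 4". Tables 10-3 and 10-4 list the thresholds.

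The table in question is introduced as "Number and percentage of subjects with treatment emergent markedly abnormal laboratory data overall (for blood chemistry and hematology". Its rule has two parts. On-treatment values from scheduled and unscheduled visits "will be included in this table summarizing markedly abnormal values". Then: "For this summary, Baseline values and values observed more than 140 days after the last administration of study medication are not considered". Section 3.1 says the same in general terms when it makes an exception for treatment-emergent markedly abnormal criteria, "where all post-Baseline (scheduled and unscheduled) values will be summarized".

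Two criteria mention Baseline. Creatinine is ">3.0 x ULN or >3.0 x Baseline" and high hemoglobin is ">40 above ULN or >40 above Baseline if Baseline is above ULN". The other thresholds in the two tables are absolute.

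**The concern.** The label says the abnormality emerged on treatment; the rule says only that it was seen on treatment. Leaving Baseline values out of the count is not the same as requiring that Baseline was not already abnormal. A subject with triglycerides above 5.7 mmol/L or glucose above 13.9 mmol/L both before and after the first dose is tabulated as a treatment-emergent case although nothing changed.

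Two things are at stake. Conditions that predate dosing are described as arising on treatment. And if a similar share of each arm carries such an abnormality, a common background is added to both percentages, which pulls any ratio between the arms toward 1.

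**Working it through.** The SAP states no figure to reproduce here. The point is one of definition, so the rules are compared first and a size is then illustrated.

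**1. How the SAP treats a pre-existing, unchanged abnormality**

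| Output | Condition | Unchanged since before first dose: counted? |
|---|---|---|
| Treatment-emergent AE (Section 10.2) | onset at or after first dose, up to 140 days after last dose | No |
| Markedly abnormal blood pressure (Table 10-6) | threshold and a minimum change from Baseline, e.g. systolic above 180 mmHg and a rise of at least 20 | No |
| Markedly abnormal laboratory value (Section 10.3, Tables 10-3 and 10-4) | threshold at any on-treatment assessment | Yes, for nearly all criteria |

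**2. Do the two Baseline clauses close the gap?**

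- Creatinine: the two legs are joined by OR. A subject at 3.5 x ULN before and after dosing meets the first leg without any change.
- High hemoglobin: this is the only criterion that makes allowance for a Baseline that is already high.

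**3. Illustration of size (all rates assumed)**

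Inputs: planned group sizes of 260 BKZ and 130 placebo (Section 2.4). Assumed: new incidence i of 3% on BKZ and 1% on placebo, and a share b of each arm already markedly abnormal at Baseline, still so afterwards and not worse.

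Reported rate r = b + (1 - b) x i.

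For b = 1%:

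- BKZ: 0.01 + 0.99 x 0.03 = 0.0397, or 260 x 0.0397 = 10.3 subjects. Of these 260 x 0.01 = 2.6 are pre-existing, i.e. 0.01/0.0397 = 25%.
- Placebo: 0.01 + 0.99 x 0.01 = 0.0199, or 130 x 0.0199 = 2.6 subjects, of whom 1.3 are pre-existing.
- Ratio: 0.0397/0.0199 = 1.99, against 3.00 for new cases only.
- Difference: 0.0397 - 0.0199 = 0.0198, against 0.0200.

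| b | Reported BKZ | Reported placebo | Ratio | Difference |
|---|---|---|---|---|
| 0% | 3.00% | 1.00% | 3.00 | 2.00 points |
| 0.5% | 3.485% | 1.495% | 2.33 | 1.99 points |
| 1% | 3.97% | 1.99% | 1.99 | 1.98 points |
| 2% | 4.94% | 2.98% | 1.66 | 1.96 points |
| 5% | 7.85% | 5.95% | 1.32 | 1.90 points |

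Counting only new cases restores the ratio to 3.00 whether the denominator is the whole arm or only those not abnormal at Baseline, because the factor (1 - b) cancels.

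**The case against.** The rule is explicit, and two programmers would build the same table from it. That is true; the fault lies between rule and label, which is why retitling is an acceptable minimum.

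Other safety outputs also count values without reference to Baseline: the absolute QTc categories in Section 10.4.2 and the AST/ALT multiples of ULN in Section 10.3. Those outputs are not described as treatment emergent, so they do not excuse this one.

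Pre-existing abnormality can be seen elsewhere: values and changes by visit, shifts in grade from Baseline, and listings of markedly abnormal results. This helps a careful reader. But the shift tables use CTCAE version 4.03 while this table uses RCTC grades, so they do not correct its counts, and listings allow only subject-by-subject reconstruction.

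A rule that excluded everyone abnormal at Baseline would lose safety information, since the table pools Grades 3 and 4 and a subject going from 3 to 4 on drug would disappear from the count. This stands, and the fix must provide for it.

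A reader might infer that a real drug signal is being diluted. The SAP does not support that: it gives no Baseline prevalence, plans only numbers and percentages by arm with no ratio or test, and the difference between arms hardly moves. A reader might also extend the point to the liver enzyme table (Table 10-5), for example to GGT above 5 x ULN. That table is not labelled treatment emergent, and it refers to CTCAE Grade 3 thresholds, which are on the same scale as the planned shift tables.

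**Conclusion.** The point holds for the chemistry and hematology table built on Tables 10-3 and 10-4. Its label promises emergence and its rule delivers any on-treatment occurrence, which departs from the SAP's own treatment-emergent AE and blood pressure rules. Nothing elsewhere in the SAP supplies the missing Baseline condition.

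The size is unknown. The illustration rests on assumed incidence and on an assumed equal Baseline share in both arms; eligibility limits in the protocol, not seen here, could make that share small for some parameters. The subject counts and any between-arm ratio are affected, the risk difference scarcely, and nothing changes if no subject is markedly abnormal at Baseline. This is a reporting correction worth making before the tables are produced. It does not show that a safety signal would be missed, and the liver enzyme table needs no correction on this ground.

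**What to change.** In Section 10.3, for the chemistry and hematology table, count a subject as treatment emergent for a criterion only if either

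- the Baseline value did not already meet that criterion in the same direction, or
- the RCTC grade worsened from Baseline, for example from Grade 3 to Grade 4.

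Show subjects already markedly abnormal at Baseline who did not worsen in a separate row, so that no one is lost from view. Because Tables 10-3 and 10-4 give one set of thresholds for Grades 3 and 4 together, the cut-off between the two grades has to be written in or referenced for the second condition to be programmed.

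At minimum, keep the present rule and retitle the table as any post-Baseline markedly abnormal value. A Baseline-abnormal row in the Table 10-5 liver table is optional.

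Cost: a short addition to the SAP, one Baseline flag in the laboratory dataset and an extra table row. The treatment-emergent counts become slightly smaller.

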10.4 Vital signs, physical findings, and other observations related to safety

10.4.1 Vital signs, weight and physical findings

The following results will be tabulated for all vital sign variables (systolic blood pressure (mmHg), diastolic blood pressure (mmHg), and pulse rate (beats/min), by treatment group and visit:

- A summary of the absolute and change from Baseline value

- A summary of the number and percentage of subjects experiencing at least one markedly abnormal value for a vital sign variable as defined in [Table 10–6](#).

Table 10–6: Definitions of markedly abnormal blood pressure values

Parameter (unit)	Markedly abnormal low	Markedly abnormal high
Systolic blood pressure (mmHg)	<90 and a decrease from Baseline of ≥ 20	>180 and an increase from Baseline of ≥ 20
Diastolic blood pressure (mmHg)	<50 and a decrease from Baseline of ≥ 15	>105 and an increase from Baseline of ≥ 15

For the Baseline visit where several BP assessments are taken, the individual observed data assessments as well as the mean of these assessments will be summarized and listed (pre-dose, 30 min post-dose and 1-hour post-dose).

Treatment-emergent markedly abnormal values will be analyzed on the SS.

Vital signs measurements will also be listed by visit and timing relative to dosing including changes from Baseline. The listing will also include details of abnormal value based on flags as defined in [Table 10–6](#) (“L” for markedly abnormal low and “H” for markedly abnormal high).

Similarly, physical examination findings together with the details of abnormalities (when applicable) will be listed by treatment group, subject and visit.

Body weight will also be listed.

10.4.2 Electrocardiograms

Since it is only planned to assess electrocardiogram (ECG) at the Screening Visit, the Baseline value will be derived based on the Screening assessment.

A summary of the absolute and change from Baseline values at Week 16 and at SFU in each ECG variable will also be created by treatment group. The following ECG variables will be assessed:

- Heart Rate (bpm)
- PR interval (ms)
- RR interval (ms)
- QRS duration (ms)
- QT interval (ms)
- QTcF interval (ms)
- QTcB interval (ms)

The date and time of the ECG will be recorded in the eCRF together with the Investigator interpretation. A summary of the number and percentage of subjects with normal, abnormal not clinically significant, and abnormal clinically significant ECG results will be presented for Baseline, Week 16 and SFU timepoints.

QTc outliers are defined as QTcF (or QTcB) values following dosing that are greater than 450 ms or are increases from Baseline greater than 30 ms. QTcF and QtcB outliers will be summarized in a dedicated table using the following categories:

- Values >450 ms, >480 ms, >500 ms
- Increase from Baseline of >30 ms, >60 ms, >90 ms
- Values >450 ms and increase of >30 ms. Values >500 ms and increase from Baseline >60 ms.

Number and percentage of subjects who meet the ECG outlier criteria at any assessment post first dose will be summarized.

All ECG tables will be provided on the SS by randomized treatment.

All 12-lead ECG data where QTcF and QTcB outliers are highlighted will also be listed.

10.5 Other safety variables

10.5.1 Electronic Columbia Suicide Severity Rating Scale (eC-SSRS)

The eC-SSRS is an assessment tool that evaluates suicidal ideation and behavior.

The eC-SSRS contains 9 categories with binary responses (yes/no):

- Category 1 - Wish to be dead
- Category 2 - Non-specific active suicidal thoughts
- Category 3 - Active suicidal ideation with any methods (not plan), without intent to act
- Category 4 - Active suicidal ideation with some intent to act, without specific plan
- Category 5 - Active suicidal ideation with specific plan and intent
- Category 6 - Preparatory acts or behavior
- Category 7 - Aborted attempt
- Category 8 - Interrupted attempt
- Category 9 - Actual attempt

Following composite endpoints based on the above categories are defined as:

- Suicidal ideation: A “yes” answer at any time during treatment to any one of the five suicidal ideation questions (Categories 1-5).
- Suicidal behavior: A “yes” answer at any time during treatment to any one of the four suicidal behavior questions (Categories 6-9).
- Suicidal ideation or behavior: A “yes” answer at any time during treatment to any one of the nine suicidal ideation and behavior questions (Categories 1-9).

Self-injurious behavior without suicidal intent is defined as event in the category non-suicidal self-injurious behavior (in category 9).

The visit identification for each assessment of eC-SSRS will not be part of the data collected and the visit date in eCRF will then be used to assign a visit identification to the eC-SSRS data.

For each subject, eC-SSRS assessment dates will be compared to eCRF visit dates.

In the Study Data Tabulation Model (SDTM):

If an eC-SSRS assessment date is matching an eCRF scheduled visit date, then the eC-SSRS visit identification will be the one corresponding to eCRF visit date. Otherwise, the eC-SSRS visit identification will be considered as “unscheduled”.

In the analysis data sets (ADaM):

If an eC-SSRS assessment date is matching an eCRF scheduled visit date within a window of +/- 3 days, then the eC-SSRS visit identification will be the one corresponding to the eCRF visit date. Otherwise, the eC-SSRS visit identification will stay as “unscheduled”.

The incidence of subjects with suicidal ideation, suicidal behavior, suicidal behavior or ideation, and self-injurious behavior without suicidal intent will be summarized by treatment and by visit for the SS. A by-subject listing of the eC-SSRS questionnaire data will be provided.

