Therefore, in order to avoid issues caused by inaccurate floating point representation of numeric values, temporary variables are created (ie, for absolute values, change and percentage change from Baseline) during programming which are rounded to 12 decimal places prior to comparison to a specific threshold in the derivation of a response parameter. This does not imply inherent rounding on the analysis variables for absolute value, change or percentage of change which are retained unrounded in the final analysis dataset. Thus, rounding is applied exclusively during the derivation of new response parameters or critical value variables, and the rounded values are created on a temporary basis only.

The SAS® outputs supportive of any inferential statistics that are part of the hierarchical testing procedure (ie, all inferential statistics associated with the endpoints in [Table 7–4](#) will be provided as a separate PDF document in addition to TFLs. These outputs will be included in the ‘Documentation of Statistical Methods’ section of the clinical study report.

The order of treatment groups to be presented in tables from left to right will be:

- Placebo
- Bimekizumab 160mg Q4W

Selected tables may also include columns for all subjects (regardless of study treatment).

The abbreviation for bimekizumab is BKZ and will be used in tables and listings headers. In the TLFs subjects randomized to bimekizumab 160mg will be labeled as “BKZ 160mg Q4W”.

Per protocol, visit windows of ± 3 days from the first dose at all visits through Week 16 are permissible. For the SFU Visit, the visit should occur no more than 3 days prior to the scheduled visit date and within 7 days after the scheduled visit date. Only data collected at the scheduled visit will be included in the analysis. The only deviation may concern unscheduled vendor data as explained in [Section 10.5](#).

All by-visit summaries will contain nominal (ie, scheduled) visits only. Unscheduled visits will not be mapped to scheduled visits except for some assessments that may occur within 3-day time window of a scheduled visit. In that case, the assessment will be mapped to the corresponding scheduled visit and will be used for the analysis unless the data are present for that scheduled visit.

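### The eC-SSRS endpoints count a yes at any time during treatment, but the only summary specified is by nominal visit, so an on-treatment yes outside the ±3-day window enters no row of the incidence table

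*SAP*

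**What the plan says.** Section 10.5.1 sets three composite endpoints at subject level. The combined one is a yes "answer at any time during treatment to any one of the nine suicidal ideation and behavior questions"; ideation (categories 1 to 5) and behavior (categories 6 to 9) are worded in the same way. None is restricted to scheduled visits.

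The eC-SSRS data carry no visit label, so the section derives one from dates. In the analysis datasets, "If an eC-SSRS assessment date is matching an eCRF scheduled visit date within a window of +/- 3 days", the assessment takes that visit's label. For every other assessment the rule is "Otherwise, the eC-SSRS visit identification will stay as" unscheduled.

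One summary and one by-subject listing follow. The incidence of ideation, behavior, either of these, "and self-injurious behavior without suicidal intent will be summarized by treatment and by visit for the SS".

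Section 3.1 supplies the general rules. On tables: "All by-visit summaries will contain nominal (ie, scheduled) visits only". On extra assessments: "Assessments collected at unscheduled visits will only be listed, except in the case of determining treatment-emergent markedly abnormal criteria for laboratory and vital sign" parameters. It also remarks, of its restriction to scheduled-visit data, "The only deviation may concern unscheduled vendor data as explained in" section 10.5.

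**The concern.** The definition and the output do not match. The definition asks whether a subject ever answered yes while on treatment. The output shows, visit by visit, who answered yes at an assessment that could be tied to a scheduled visit. A subject whose only yes falls four or more days from any scheduled visit satisfies the first and is absent from the second.

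At stake is the accuracy of a descriptive safety table. A reader of the study report would take the eC-SSRS incidence to be the endpoint as defined, when it leaves out part of the data on which the endpoint rests.

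**Working it through.** No sample size, power or error rate is involved, and the SAP gives no figure to reproduce. The check is to follow one assessment through the rules.

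1. **Hypothetical case.** A treated subject answers yes to an ideation question at an eC-SSRS completed 42 days after first dose. The neighbouring scheduled visits are Week 4 (28 days) and Week 8 (56 days). The distances are 42 − 28 = 14 days and 56 − 42 = 14 days, both more than 3.
2. **Endpoint definition (10.5.1).** The answer was given during treatment, so the subject meets suicidal ideation and also ideation or behavior.
3. **Visit label (10.5.1).** No scheduled visit date lies within 3 days, so the assessment stays unscheduled.
4. **Summary (10.5.1 with 3.1).** The table is by treatment and by visit, and by-visit tables hold nominal visits only. The assessment has no nominal visit, so no row takes it.
5. **Exceptions (3.1).** The exception for unscheduled assessments covers markedly abnormal laboratory and vital sign values. The eC-SSRS is not named.
6. **Vendor-data remark (3.1).** It refers to section 10.5, where the only provision on unscheduled data is the ±3-day mapping already applied in step 3. It says nothing on assessments outside the window.
7. **Result.** The subject meets the endpoint and appears in the listing, but not in the incidence table.

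Two further observations:

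- Visit rows cannot be added to give the number of subjects with any yes, because one subject may be positive at several visits. Even if every assessment were on schedule, the ever-yes count would not be among the outputs the section specifies.
- The SAP says so elsewhere when it wants unscheduled values counted. Section 10.3 includes laboratory values from scheduled and unscheduled visits and excludes those more than 140 days after last dose. Section 10.4.2 counts ECG outliers at any assessment after first dose. Section 10.5.1 has no comparable sentence.

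On direction: leaving out a positive assessment can lower the number of subjects with a yes and can never raise it. With the Safety Set as denominator, the incidence can therefore only be understated.

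**The case against.** The strongest reply is that by treatment and by visit may mean an overall figure per arm plus a breakdown by visit. An any-time composite makes little sense without the overall figure, and the specific wording of 10.5.1 could be held to prevail over the general listing rule. The vendor-data remark also shows that the authors had unscheduled eC-SSRS data in mind. This is a fair account of what may have been intended. But the SAP neither states an overall row nor says which assessments would feed it, and the remark leads only to the mapping rule. A programmer who follows the text would leave the assessment out.

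The second reply is that little is lost, and part of this stands. The responses are listed. Suicidality reported as an adverse event can reach the adjudicated table in 10.2.4.5, which does not depend on eC-SSRS visit mapping. That table rests on events judged by a committee, however, not on questionnaire answers, so it does not deliver the endpoint of 10.5.1.

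A reader might also infer more than the SAP supports:

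- **That suicidality between visits goes uncounted altogether.** The gap is confined to the eC-SSRS incidence table.
- **That a known, large share of assessments is lost,** by setting the window against the four-week visit spacing. That assumes randomly timed extra assessments; the SAP does not say that any are expected, or when.
- **That the omitted assessments are more likely to be positive.** This is plausible if concern prompts them, but the SAP gives no basis for it.
- **That the treatment comparison would change.** No inferential eC-SSRS comparison is planned.
- **That the long gap before the Safety Follow-Up visit makes it worse.** The composites are limited to treatment, and 10.5.1 does not say that this extends into follow-up.

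**Conclusion.** The point stands as an inconsistency between an endpoint definition and its only specified summary. Applied literally, the plan omits an on-treatment yes outside the ±3-day window from the eC-SSRS incidence table, and the omission works in one direction only. Its size is unknown: the SAP does not give the number of out-of-window assessments or of subjects affected, and it may be zero.

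The conclusion rests on reading the summary sentence as a by-visit table governed by section 3.1. If an overall row was intended, the defect reduces to an unstated row and an unstated data rule, and the same correction applies. It is worth correcting because the table concerns safety and the remedy is small. It does not touch the efficacy conclusions or the adjudicated suicidality outputs.

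**What to change.** In 10.5.1, add an overall row per arm: the number and percentage of subjects with at least one yes (ideation, behavior, either) at any on-treatment eC-SSRS after first dose, scheduled or unscheduled. State what during treatment means for this row. One option is the cut-off of 140 days after last dose that 10.3 already uses for on-treatment laboratory values; the choice is the sponsor's, since 10.5.1 gives none now. In 3.1, add the eC-SSRS to the exception for unscheduled assessments. Keep the by-visit table as it is.

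The cost is a few sentences in the SAP and one extra block of rows in an existing table, from data already collected and listed.
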